#### 11.4 DEATHS

All deaths occurring within 30 days of study TDE-PH-304 participation will be listed by subject, including previous study, first dose, last dose, discontinuation date, reason for discontinuation, date of death, day of death, and cause of death. The summary of deaths will be presented by previous study and overall and will include the number (percent) of subjects who died within 30 days of study participation and their causes of death.

#### 11.5 CLINICAL LABORATORY TESTS

All clinical laboratory data from the parent studies and from study TDE-PH-304 will be incorporated in these laboratory listings and summaries. The laboratory data will be listed by subject and previous study, including all hematology and clinical chemistry parameters by scheduled time point. Each parameter will include its respective normal range in the row label. A designation for low (L) and high (H) will be included for those laboratory values that are outside the normal range. The listing of urinalysis will also be presented by subject and previous study and will include each scheduled and unscheduled urinalysis assessment. The date/time, study day, and window will be provided for each assessment as well as the result of the test.

Plots will be generated for both hematology and clinical chemistry shifts from baseline. For each parameter, two plots will be generated displaying baseline values on the x-axis and minimum/maximum values on the y-axis, respectively. The plots will be scatter plots that utilize a different plotting symbol for each previous study denotation. A line of unity will be overlaid on the plot to aid in understanding the shift from baseline for each parameter.

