7 EXPERIMENTAL PROCEDURES

7.1 Open-Label Phase

All values collected at the subject's respective final visit in protocol TDE-PH-202 TDE-PH-203, TDE-PH-205, TDE-PH-301 or TDE-PH-308 and TDE-PH-302 will serve as the baseline assessments for the open-label study.

Subjects receiving placebo in the previous study must be contacted weekly by telephone (at a minimum) during the first 12 weeks of the open-label study and, if necessary, brought in for clinic visits in the first several months of the study to ensure subject safety. This also applies to subjects enrolled from the TDE-PH-202 study (Dose Groups 1 or 2) who are beginning a dose of 0.25mg BID.

Monthly telephone calls (at a minimum) must be conducted for all subjects actively participating in the open-label study, regardless of study drug allocation (UT-15C SR or placebo) in the previous study.

In addition to the scheduled study visits, as listed below, all subjects must be seen in the clinic no less than once every six months for routine standard of care medical evaluation.

Weekly telephone calls (required Weeks 1-12; only for subjects randomized to placebo in previous study). This also applies to subjects enrolled from the TDE-PH-202 study (Dose Groups 1 or 2) who are beginning a dose of 0.25mg BID.

- Adverse events
- PAH concomitant medications
- Concomitant medications

Drug accountability / compliance

Weekly telephone calls (required for 4 weeks for subjects who transition from BID to TID dosing)

- Adverse Events
- PAH concomitant medications
- Concomitant medications
- Drug accountability/compliance

Monthly telephone calls (required for all subjects participating in open-label study)

- Adverse events
- PAH concomitant medications
- Concomitant medications
- Drug accountability / compliance

Visit 1 (three months after first dose of UT-15C SR; only for subjects randomized to placebo in previous study). This also applies to subjects enrolled from the TDE-PH-202 study (Dose Groups 1 or 2) who are beginning a dose of 0.25mg BID.

- Adverse events
- PAH concomitant medications
- Concomitant medications
- Clinical laboratories
- Drug accountability/compliance

Visit 2 (six months after first dose of UT-15C SR)

- Adverse events
- PAH concomitant medications
- Concomitant medications
- Clinical laboratories
- Drug accountability/compliance

Visit 3 (12 months after first dose of UT-15C SR)

- Adverse events
- PAH concomitant medications
- Concomitant medications
- Clinical laboratories

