#### **7 ANALYSIS POPULATIONS**

All available data from all subjects enrolled in the TDE-PH-304 study will be used as detailed in this analysis plan. Additionally, subjects who were treated with active drug during the parent study and who enrolled in the TDE-PH-304 study will have the data from the parent study included in the data analyses and listings for this study, as detailed in this SAP.

Subjects who were treated with placebo during the parent study and who enrolled in the TDE-PH-304 study will have baseline data only from the parent study included in the data analyses and listings for this study, as detailed in this SAP.

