## **8 GENERAL CONSIDERATIONS FOR DATA ANALYSES**

All available data for subjects enrolled in TDE-PH-304 (regardless of treatment with active drug) will be included in each soft lock and will be listed. All available data for enrolled subjects who were treated with active drug in study TDE-PH-304 will be summarized, as detailed in this SAP. Subjects from the 200 series studies (TDE-PH-202, TDE-PH-203, and TDE-PH-205) that enrolled into the TDE-PH-304 study will be pooled for summarization purposes with the two de novo subjects previously enrolled in the TDE-PH-301 study. These two de novo subjects were initially enrolled in TDE-PH-301, but were later withdrawn from that study following a temporary drug recall in June 2006 and were subsequently directly enrolled in the TDE-PH-304 OL study. Likewise, subjects from studies TDE-PH-301 and TDE-PH-308 will be pooled for summarization purposes.

In general, listings will be sorted by subject number and scheduled assessment (if applicable). Listings will include assessment date, assessment time (if available), and study day. For data collected on a fixed schedule, the assessment identifier will also be included on the listing.

In general, the data will be summarized by scheduled assessment (if applicable). For continuous variables, the summary statistics will include the mean, standard deviation, standard error, median, lower quartile, upper quartile, minimum, and maximum. Minimums and maximums will be expressed using the level of precision in which the variable was collected. All other statistics will be rounded, using an additional decimal point. For discrete variables, summaries will include the frequency and percent in each category. Percentages will be rounded to a whole number. Whenever practical, categories of discrete variables will be ordered and labeled as they appear in the case report form (CRF), and all categories represented on the CRF will be included in summaries, even when they do not apply to any subjects in the study.

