## 11 SAFETY ANALYSES

### 11.1 EXTENT OF EXPOSURE

Study drug exposure will be listed, including subject number, previous study, concomitant medication use, BID to three times daily (TID) transition, exposure (weeks), and categorical exposure (by visit). Exposure is calculated as the time exposed to active study drug. For subjects treated with active drug during the parent study, exposure calculations will include their exposure during the parent study. For subjects treated with placebo during the parent study, exposure calculations will include only the exposure to active drug during the OL study. The summary of disposition and study drug exposure will detail the number (percent) of subjects who died during the study, as well as the study drug exposure both by categorical visits ( $\geq 3$  months,  $\geq 6$  months, etc.) and using descriptive statistics. The total study drug exposure (pt-years) will also be displayed.

Study drug dosing will be summarized at each visit by previous study and overall. The summary will include a categorical summary of current status (in study, death, progression of PAH, AE, consent withdrawn, lost to follow-up, discontinued for other reasons, etc.) and study drug dose (<1 mg, 1-<2.5 mg, 2.5-<5 mg, 5-<10 mg, 10-<20 mg, 20-<30 mg BID/TID), as well as a descriptive statistics summary of study drug dose (mg BID/TID).

Study drug dosing will also be summarized at each visit by PAH background medication use, grouping subjects into monotherapy and combination therapy groups. The summary table will mimic that presented in the summary of study drug dosing by previous study, but will produce a separate summary table for each PAH background medication use group.

The summary of BID to TID transition will detail the number (percent) of subjects who completed this transition and who had to transition back to BID (if applicable), and descriptive statistics on the doses both before and after the transition by previous study and overall. All of these summaries will be provided by previous study and overall.

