## 11.2 ADVERSE EVENTS

Adverse event summaries will include treatment emergent AEs. Treatment emergent AEs include those reported during the parent study for those subjects who were treated with active drug during the parent study. For subjects treated with placebo during the parent study, only those AEs reported during the TDE-PH-304 study are considered treatment emergent.

The AEs will be coded using the Medical Dictionary for Regulatory Activities (MedDRA) and all summaries will utilize the preferred term (PT) and/or System Organ Class (SOC). The correspondence of raw AE terms to PTs and SOCs will be listed. All AEs and serious AEs will be listed by subject, including onset date/day, cessation date/day, verbatim term, PT, SOC, seriousness, severity, relationship to study drug, frequency, and action taken with study drug. The summaries of AEs will be provided by previous study and overall. The summaries of AEs, serious AEs, severe AEs, AEs reasonably or possibly related to study drug, and AEs leading to permanent discontinuation of study drug will include the number of subjects (percent of subjects) and number of events for each reported PT. The summary of AEs by body system will include the same statistics, but will group the PTs by their respective SOCs.

The summary of AEs by exposure will include the number of subjects (percent of subjects) and number of events for each reported PT, as well as the number of events per patient year of exposure. Note that only those subjects with calculated exposure will have AEs contributing to this summary.

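### SAP 11.5 brings all parent-study laboratory data into the laboratory outputs, while SAP 7 admits only baseline data for subjects who took placebo in the parent study

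*SAP*

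**What the plan says.** **Scope of laboratory data.** SAP 11.5 opens with "All clinical laboratory data from the parent studies and from study TDE-PH-304 will be incorporated in these laboratory listings and summaries". Treatment in the parent study is not mentioned.

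**General rule.** SAP 7 admits the parent-study data of subjects who took active drug there. Subjects who took placebo there "will have baseline data only from the parent study included in the data analyses and listings for this study, as detailed in this SAP".

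**Sister sections.** SAP 11.1: "For subjects treated with placebo during the parent study, exposure calculations will include only the exposure to active drug during the OL study". SAP 11.2: "For subjects treated with placebo during the parent study, only those AEs reported during the TDE-PH-304 study are considered treatment emergent".

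**Shift outputs.** For each hematology and chemistry parameter, SAP 11.5 says that "two plots will be generated displaying baseline values on the x-axis and minimum/maximum values on the y-axis, respectively". No period is given for the extremes. SAP 12.2 also lists two shift tables (14.3.4.2 and 14.3.4.4) by title, and 11.5 does not describe them.

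**Baseline.** Protocol 7.1 says that all values from the final parent-study visit "will serve as the baseline assessments for the open-label study". For laboratories, the SAP neither adopts nor replaces this.

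**Presentation.** SAP 8 summarises data in general by scheduled assessment, and SAP 8.1 by previous study and overall. SAP 8 adds that "subjects from studies TDE-PH-301 and TDE-PH-308 will be pooled for summarization purposes". SAP 8 also says that all available data for enrolled subjects will be listed, whether or not they were treated with active drug.

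**The concern.** Laboratory parameters are one of two named safety endpoints (SAP 2.2), and Protocol 10 uses them to assess the safety of UT-15C SR. For a post-baseline value taken on placebo in the parent study, SAP 7 says leave it out and SAP 11.5 says put it in. A programmer who follows 11.5 would report laboratory values from a period that the exposure and adverse event outputs exclude for the same subjects.

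The summaries would not separate such values by arm. Table columns and plot symbols are by previous study, and two of the placebo-controlled studies are pooled. SAP 10.1 splits six-minute walk distance by parent treatment; no such split is planned for laboratories. SAP 5 foresees interim analyses for regulatory submissions and as often as yearly, so an unresolved choice could also be programmed differently from one data cut to the next.

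**Working it through.** The documents state no figure on this point, so there is nothing to reproduce. The check compares the text and counts outputs.

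**1. Outputs and studies affected** (SAP 12.2 to 12.4; Protocol Summary)

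- Laboratory tables 14.3.4.1 to 14.3.4.5: 5.
- Laboratory listings 16.2.8.1 and 16.2.8.2: 2.
- Shift figures 14.3.4.1 and 14.3.4.2: 2. The opening sentence of 11.5 names listings and summaries; I take the figures to draw on the same data.
- Total: 5 + 2 + 2 = 9. Shift outputs: 2 tables + 2 figures = 4.
- Parent studies named: 202, 203, 205, 301, 302 and 308 = 6. With placebo subjects: 301, 302 and 308 = 3.

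**2. A parent-placebo subject.** In time order, call the values B (parent-study baseline), P (later values on placebo), F (final parent visit) and O (open-label visits on UT-15C SR). SAP 7 admits one baseline and O. SAP 11.5 admits B, P, F and O. The two differ on P, and on whichever of B and F is not the baseline.

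**3. Can P reach the shift outputs?**

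| Reading | Placebo-period value as minimum or maximum? |
|---|---|
| SAP 7 governs, extremes taken after baseline | No |
| SAP 11.5 literal; baseline F (Protocol 7.1); later values only | No |
| SAP 11.5 literal; extremes over all included values | Possible |
| SAP 11.5 literal; baseline B; all later values | Possible |

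The SAP does not choose among these.

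**4. Can P reach the by-visit tables?** SAP 3 times TDE-PH-304 visits from first UT-15C SR, so a placebo draw has no TDE-PH-304 visit to fall into. It appears only if parent visits are shown as rows. Such a row would combine placebo and on-drug draws from the same parent study. The SAP does not say whether these rows exist.

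**5. Listings.** Under 11.5 the values are listed. They can be identified by comparing the assessment date (SAP 8) with the first active-dose date (SAP 9.1).

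**6. A parent-active subject.** Here F is normally an on-drug value. With F as baseline and later values only, none of the earlier on-drug parent data that SAP 7 admits can enter a shift. With F as baseline and all values included, values from before baseline could supply a shift from baseline. A last value before first active dose avoids both.

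**7. A date filter alone is not enough.** Under Protocol 3.1 and 3.5, TDE-PH-202 Dose Group 1 or 2 subjects who stopped drug for clinical worsening could complete visits to Week 12 and start again in TDE-PH-304. Their values between stopping and restarting are off drug, yet fall after first active dose.

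**The case against.** The strongest reply is that SAP 7 is the population section, so the word all in 11.5 means all the parent data that SAP 7 lets in. On that reading no placebo value beyond baseline is used. This is plausible, but the text does not settle it. SAP 7 closes by deferring to the detail elsewhere in the SAP, which lets 11.5 be read as the governing detail. SAP 11.1 and 11.2 restate the placebo rule where it applies; 11.5 does not. If 11.5 is a deliberate exception, it is not labelled as one.

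Other parts of the reply stand:

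- A reader might infer that the shift plots will be contaminated because no baseline exists. The documents do not support that. SAP 1 presents the SAP as adding detail to the planned analyses, and Protocol 7.1 supplies a baseline that covers laboratories. With that baseline and later values only, placebo values stay out of the shifts except as baseline. The missing shift period is therefore secondary.
- Placebo values would not merge into open-label visit rows. Only parent-visit rows could mix the arms.
- The SAP 8 sentence on listing all available data may support broad listings. It can also be read as describing which subjects are listed, not which period. It does not extend to the summaries.
- The outputs are descriptive, and no laboratory test is planned.

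**Conclusion.** The contradiction is real. As written, SAP 11.5 overrides the SAP 7 restriction and departs from the placebo exclusions in 11.1 and 11.2. It should be corrected, because it is a stated rule that conflicts with another and not only a missing detail. Taken literally, it allows placebo-period values into UT-15C SR laboratory listings, into any parent-visit rows, and into the shift minima and maxima if these span all included values or start from the parent study's own baseline.

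The size cannot be computed. A reader might want a percentage of plotted extremes that come from placebo time. That would need the number of parent laboratory draws, which the documents do not give, and an assumption about how values behave over time. No such figure is supported. What can be stated is the reach: nine outputs, four of them shift outputs, and three of six named parent studies. For the four shift outputs the effect is nil under either of two readings: SAP 7 governs, or the Protocol 7.1 baseline is used with later values only.

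Confidence is high on the mismatch in the text. How much it would change the reported laboratory results is unknown.

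**What to change.** 1. Replace the opening sentence of SAP 11.5 with, for example: *Laboratory data from TDE-PH-304 are included. Parent-study laboratory data are included as specified in Section 7: every value for subjects who took active drug in the parent study, and the baseline value alone for subjects who took placebo.*
2. For the shift tables and plots, define baseline as the last value before the first dose of active drug. For parent-placebo subjects this is the final parent-study visit, in line with Protocol 7.1. For parent-active subjects it is a pre-drug value from the parent study, and Protocol 7.1 must be reconciled with it.
3. Take minima and maxima only from values after the first active dose. With the baseline in item 2, the on-drug parent data that SAP 7 admits are kept.
4. Flag the off-drug values of TDE-PH-202 Dose Group 1 or 2 subjects who stopped and restarted, or handle them by a stated rule.
5. If placebo-period values are to be listed, reconcile Section 7 with the SAP 8 listing sentence and flag those values, in the listings only.

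The cost is a short SAP edit, a filter on the first active-dose date that SAP 9.1 already lists, a rule for the restarted subjects, and one carried-over pre-drug value per parameter for each parent-active subject.

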**12 APPENDICES****12.1 INCLUSION AND EXCLUSION CRITERIA**

A subject is eligible for inclusion in this study if all of the following criteria apply:

1. The subject has remained on study drug and completed all assessments during the Treatment Phase of the previous study (TDE-PH-202, TDE-PH-203, TDE-PH-205, TDE-PH-301, TDE-PH-302, or TDE-PH-308 [or other studies evaluating PAH])

OR

The subject permanently discontinued study drug during the Treatment Phase of the previous study (TDE-PH-301, TDE-PH-302, or TDE-PH-308) due to clinical worsening, completed premature termination assessments prior to discontinuing study drug, completed all remaining scheduled study visits, AND received placebo during the Treatment Phase of the previous study (TDE-PH-301, TDE-PH-302, or TDE-PH-308).

OR

The subject was randomized into Dose Group 1 or Dose Group 2 in the TDE-PH-202, permanently discontinued study drug during the 12-week Treatment Phase due to clinical worsening, completed all premature termination assessments prior to discontinuing study drug, and completed all remaining scheduled study visits and assessments (with the exception of the hemodynamic measurements) through Week 12. Such subjects should start treatment with UT-15C in the open-label study at 0.25 mg BID.

2. The subject voluntarily gives informed consent to participate in the study.
3. Women of child bearing potential include any female who has experienced menarche and who has not undergone successful surgical sterilization (hysterectomy, bilateral tubal ligation or bilateral oophorectomy) or is not postmenopausal (defined as amenorrhea for at least 12 consecutive months). Sexually active women of childbearing potential must use two effective forms of contraception during the length of the study. Medically acceptable forms of effective contraception include: (1) approved hormonal contraceptives (such as birth control pills), (2) barrier methods (such as a condom or diaphragm) used with a spermicide, (3) an intrauterine device (IUD), (4) partner vasectomy, or (5) abstinence. Males participating in the study must use a condom during the length of the study, and for at least 48 hours after discontinuing study medication.

A subject is ineligible for inclusion in this study if any of the following criteria apply:

1. The subject permanently discontinued study drug during the previous study (TDE-PH-202, TDE-PH-203, TDE-PH-205, TDE-PH-301, TDE-PH-302, or TDE-PH-308) due to treatment related adverse events.

2. The subject permanently discontinued study drug during the Treatment Phase of the previous study (TDE-PH-202, TDE-PH-203, TDE-PH-205, TDE-PH-301, TDE-PH-302, or TDE-PH-308) due to clinical worsening (as defined in those study protocols) and did not undergo premature termination assessments prior to discontinuing study drug, and/or did not complete all remaining study visits through the final scheduled visit.
3. The subject permanently discontinued study drug during the Treatment Phase of the previous study (TDE-PH-301, TDE-PH-302, or TDE-PH-308) due to clinical worsening, completed premature termination assessments prior to discontinuing study drug, completed all remaining scheduled study visits AND received UT-15C SR during the Treatment Phase of the previous study (TDE-PH-301, TDE-PH-302, or TDE-PH-308).

Subjects enrolled in the TDE-PH-202 study who were randomized into the iMTD group who clinically worsen may not participate. Subjects who permanently discontinue study drug during the 12-week Treatment Phase due to treatment related adverse events are not eligible even if they complete all remaining scheduled study visits. Subjects who permanently discontinue study drug during the 12-week Treatment Phase and do not undergo premature termination assessments prior to discontinuing study drug and/or who do not complete all remaining study visits through the Week 12 visit are also not eligible.

4. The subject must not have developed any concurrent illness or condition during the conduct of the previous study, including but not restricted to, sleep apnea, chronic renal insufficiency, anemia, uncontrolled systemic hypertension or left sided heart disease, unless their physician feels that entry into this study would not be detrimental to their overall health.

